2.1.3 Other objectives

The other objectives of the study are to:

- Assess the effect of bimekizumab on gene and protein expression, and explore the relationship between genomic, genetic, and proteomic biomarkers and disease biology, drug treatment and inflammatory/immune responses

2.2 Study variables

2.2.1 Primary variables

2.2.1.1 Primary efficacy variable

The primary endpoint of this study is change from Baseline in PASI at Week 28.

2.2.1.2 Primary pharmacokinetic variable

The primary PK variable is plasma concentration of bimekizumab.

2.2.1.3 Primary immunogenicity variable

The primary immunological variable is anti-drug (bimekizumab) antibody (ADA) detection prior to and following study treatment.

2.2.1.4 Primary safety variable

The primary safety variable is incidence of adverse events (AEs).

2.2.2 Secondary variables

The secondary efficacy variables are:

- PASI75, PASI90 and PASI100 response at Week 16
- Investigator's Global Assessment (IGA) response (Clear or Almost Clear with at least a 2-category improvement from Baseline) at Week 16

2.2.3 Other variables

2.2.3.1 Other efficacy variables

The other efficacy variables are listed below and will be evaluated at all scheduled visits in accordance with the schedule of assessments in Table 5-1 of the clinical study protocol. This excludes the primary and secondary variables as previously specified in [Section 2.2.1](#) and [Section 2.2.2](#).

- Absolute and percentage change from Baseline in PASI with time (Week 2 to Week 36)
- PASI75, PASI90 and PASI100 response at Weeks 2, 4, 8, 12, 20, 24, 28 and 36
- PASI25 and PASI50 response (Week 2 to Week 36)
- IGA response (Clear or Almost Clear with at least 2-category improvement from Baseline) at Weeks 2, 4, 8, 12, 20, 24, 28 and 36
- Change from Baseline in IGA score with time (Week 2 to Week 36)
- Change from Baseline in the body surface area (BSA) affected by psoriasis with time (Week 2 to Week 36)
- Change from Baseline in Hospital Anxiety and Depression Scale (HADS) HADS-Anxiety (HADS-A) and HADS-Depression (HADS-D) scores with time (Week 4 to Week 36)

- Percentage of subjects with scores below 8 in HADS-A and HADS-D (subjects with normal scores) at each post-Baseline visit (Week 4 to Week 36)

2.2.3.2 Other pharmacodynamic variable

The pharmacodynamic (PD) variable is to determine the blood or blood derivative (eg, plasma) concentrations of cytokines of relevance to interleukin (IL)-17A/F signaling pathway and psoriasis biology, including but not limited to serum complement concentrations, mononuclear cell subtypes (flow cytometry), cytokines and other candidate biomarkers.

Only the results for the flow cytometry will be included in the TFLs. The results arising from the analysis of other PD variables will be reported separately, if applicable. These are not described further in this SAP.

2.2.3.3 Other safety variables

Other safety variables to be assessed are:

- Change from Baseline in clinical laboratory variables (chemistry, hematology and urinalysis)
- Change from Baseline in vital signs
- Change from Baseline in physical examination
- Electrocardiogram (ECG) results

2.2.4 Ribonucleic acid, proteins, and metabolite variables

Blood and tissue biopsy samples will be collected at specified timepoints and stored for up to 20 years to allow for potential exploratory analyses of ribonucleic acid (RNA), proteins and metabolites biomarkers relevant to psoriasis and the inflammatory and immune response process.

The nature and format of these tentative analyses will be determined at a later stage.

These results will not form part of the TFLs and therefore are not discussed further in this SAP.

2.2.5 Immunological variable

The immunological variable is ADA detection following study treatment.

2.3 Study design and conduct

This is a Phase 2a, multicenter, randomized, subject-blind and investigator-blind study to evaluate the PD, PK, and safety of bimekizumab administered via subcutaneous (sc) injection to subjects with psoriasis. To be eligible to participate in this study, subjects must be adults with a diagnosis of moderate to severe chronic plaque psoriasis (Baseline PASI ≥ 12 and BSA affected by psoriasis $\geq 10\%$ and IGA score ≥ 3 [on a 5-point scale]) who are candidates for systemic psoriasis therapy and/or phototherapy and/or chemophototherapy.

This study will include 3 periods: a Screening Period (up to 4 weeks), a Treatment Period (28 weeks), and a Safety Follow-Up (SFU) Period (20 weeks after the last dose of study medication). Between Week 20 and the end of the 28-week Treatment Period, eligible subjects will be allowed to enroll in an extension study.

Screening Period

The Screening Period will last up to a total of 4 weeks in the event that applicable laboratory screening tests require retesting if the initial results are in error, borderline, or indeterminate. During this time, laboratory data (hematology, urine, and biochemistry tests) will be obtained, the doses of non-steroidal anti-inflammatory drugs (NSAIDs) (if used to treat psoriatic arthritis), will be verified as stable.

Treatment Period

During the Treatment Period, subjects will be randomized 2:1 to receive one of the following blinded study treatment regimens:

- Treatment arm A: Bimekizumab 320mg administered sc at Baseline and Week 4, and placebo administered at Week 16
- Treatment arm B: Bimekizumab 320mg administered sc at Baseline and Weeks 4 and 16

There will be approximately 30 subjects in treatment arm A and 15 subjects in treatment arm B. Bimekizumab will be administered in the clinic at Baseline and Week 4, and at Baseline, Week 4, and Week 16 for those in treatment arm A and treatment arm B, respectively. Additional nondosing study visits will occur at Week 2, Week 8, Week 12, Week 20, Week 24, and Week 28.

From Week 20 through Week 28, subjects who were previously PASI25 responders (defined as described in [Section 8.3.1](#)) but subsequently relapse (defined as returning to a less than PASI25 response) will undergo the study assessments for that visit (ie, Week 20, Week 24, or Week 28) before receiving their first dose of study treatment in the extension study at Week 20, Week 24, or Week 28. Subjects eligible for the extension study must have the assessments for SFU (for PS0016) conducted prior to entering the extension study. Subjects may also enter the extension study after the SFU Visit at Week 36. Subjects who have not achieved a PASI25 response at any visit prior to Week 20 will not be eligible to enter the extension study. All subjects not enrolling in the extension study will continue in PS0016 until the SFU Visit at Week 36.

Subjects withdrawing early from the study will undergo the Early Withdrawal Visit (EWD) assessments (ie, the same assessments as for Week 36) and will enter the SFU Period, completing study participation with the SFU Visit 20 weeks after the last dose of investigational medicinal product (IMP).

Safety Follow-Up Period

All subjects not continuing in the extension study, including those withdrawn from study treatment, will have a SFU Visit 20 weeks after their last dose of IMP (ie, bimekizumab or placebo).

2.4 Determination of sample size

No formal statistical sample size estimation has been performed due to the exploratory nature of this study. This clinical study is not powered for any conclusive statistical analysis of efficacy, PK, safety or immunological variables. The sample size has been determined based on the number of subjects required in the current study to provide reliable PK/PD model parameter estimates when the data is combined with PS0010. Reliable estimates of PK/PD parameters are

defined as number of subjects required to achieve a relative standard error of $\leq 30\%$ for fixed effects parameters and $\leq 50\%$ for all random effects parameters.

In order to determine the sample size required for the PK/PD model, Markov chain Monte Carlo (MCMC) simulations were performed. Five hundred trials were simulated with the proposed design, and including 240 subjects from PS0010. The simulated data were re-estimated using the same model. These simulations indicated that reliable estimates will be possible with a total number of 45 subjects (30 subjects in Treatment arm A and 15 subjects in Treatment arm B).

3 DATA ANALYSIS CONSIDERATIONS

3.1 General presentation of summaries and analyses

Statistical evaluation will be performed by PAREXEL. The datasets will follow the UCB analysis data model (ADaM) data specifications.

All analyses will be performed using SAS version 9.3 or higher (SAS Institute, Cary, North Carolina, United States). Continuous variables will be summarized by treatment group, visit and timepoint (where applicable) including number of subjects (n), mean, standard deviation (SD), median, minimum, maximum and confidence intervals (CI) where stated in the SAP. Categorical variables will be summarized by treatment, visit and timepoint (where applicable) with frequency counts and percentages. Coefficient of variation (CV), geometric mean and 95% CI for the geometric mean will also be presented in the descriptive statistics for the PK concentration data. In all outputs the confidence limits will be restricted to the possible values that the variable can take.

When reporting relative frequencies or other percentage values, the following rules apply:

- For values where all subjects fulfill certain criteria, the percentage value will be displayed as 100
- For values where the absolute frequency is zero, there will be no percentage displayed at all
- All other percentage displays will use 1 decimal place

Percentages displayed based on continuous data (eg, percentage changes from baseline) will be displayed to 1 decimal place. Unless otherwise stated, the denominator for the percentages will be based on the number of subjects in the respective analysis set and treatment group.

When reporting descriptive statistics, the following rules will apply in general (with the exception of PK concentration data, for which additional rules are stated below):

- n will be an integer
- Mean (arithmetic and geometric), SD and median will use 1 decimal place more than the original data
- Coefficient of variation (CV) will be reported as a percentage to 1 decimal place
- Minimum and maximum will be reported using the same number of decimal places as the original value

- If no subjects have data at a given timepoint, for example, then only n=0 will be presented. If n<3, then only the n, minimum and maximum will be presented. If n=3, then only n, median, minimum and maximum will be presented. The other descriptive statistics will be left blank.

When reporting individual values and descriptive statistics for PK concentration data, the following rules will apply with regard to rounding and precision:

- Individual values for PK concentration data will be reported to the same level of precision as received from the bioanalytical laboratory
- Descriptive statistics for PK concentration data will be reported to the same level of precision as the individual data for the minimum and maximum, and to 1 additional significant figure for the mean (arithmetic and geometric), median, SD and 95% CI for the geometric mean
- Geometric CV (geoCV) will be reported as a percentage to 1 decimal place

All tabulations will be performed by treatment group, visit and timepoint (where applicable). In the TFLs the treatment groups will be displayed as follows where BKZ refers to bimekizumab and PBO refers to placebo:

- BKZ 320mg + PBO
- BKZ 320mg

Data listings containing all documented data and all derived data will be generated.

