3.5.3 Safety Set

The Safety Set (SS) will consist of all subjects who received at least 1 dose of the study medication.

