11 SAFETY ANALYSES

All analysis of safety variables will be performed using the SS, unless otherwise stated.

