11.3 Clinical laboratory evaluations

Laboratory data (clinical chemistry, hematology, and urinalysis) and changes from Baseline (if applicable) for numeric variables will be listed by treatment group and visit. Any laboratory variables with values that are BLQ or ALQ will be handled as described in [Section 4.2.2](#) for calculation of changes from Baseline and for summary tables. Values outside the reference range for the numeric variables will be flagged in the listings and in addition, will be listed separately. The reference ranges will also be reported in the listings.

Clinical chemistry and hematology variables will be summarized by treatment group (including All Subjects) at each visit, for both absolute values and changes from Baseline.

Laboratory variables will be grouped according to the laboratory function panel and categorized as normal, high or low, if applicable, based on the reference range supplied by the analytical laboratory. For selected variables that are identified in [Table 11-1](#), the change in category from Baseline will be presented in shift tables at all post-Baseline visits.

The number and percentage of subjects with treatment-emergent markedly abnormal (TEMA) laboratory results (to match the TEAE definition stated in [Section 11.1.3](#)) will be tabulated by treatment group and visit. Markedly abnormal laboratory values will be defined as those categorized as Grade 3 and above based on the ranges defined as per the Common Terminology Criteria for Adverse Events (CTCAE) Version 4.03 (2016). These are provided in [Table 14-4](#). The tabulation will include a category for the incidence of TEMA results over all visits which will also count unscheduled measurements.

In addition, for absolute neutrophil count (ANC), all grade 2 CTCAE abnormalities ($<1.5 - 1.0 \times 10^9/L$) will be listed separately, with results from all visits for any subject that has any grade 2 abnormality.

Laboratory measurements meeting the criteria for TEMA will be listed separately for hematology and chemistry. The listings will include all measurements for any variable with at least one TEMA result for each subject.

Any additional laboratory variables not included in the outputs described previously will be listed separately. These will include the following:

- Serology
- Pregnancy tests (serum and urine)
- Follicle stimulating hormone (FSH) (only for postmenopausal women)

The results of the Quantiferon TB Gold test will be listed separately.

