11.4 Vital signs, physical findings, and other observations related to safety

11.4.1 Vital signs

The following vital signs measurements will be obtained:

- Pulse rate
- Systolic and diastolic blood pressure
- Temperature (oral or otic)

A by-subject listing of all vital sign measurements and changes from Baseline will be presented by treatment group and visit. The listing will include a flag for measurements identified as TEMA/potentially clinically significant (PCS) as calculated by the criteria outlined in [Table 14–6](#).

Descriptive statistics will be reported for all vital sign measurements. Measured values and changes from Baseline will be summarized by vital signs variable and visit for each treatment group.

The number and percentage of subjects with TEMA/PCS vital sign values (to match the TEAE definition stated in [Section 11.1.3](#)) will be summarized by treatment group (including All Subjects) and variable at each visit and overall (ie, across all post-Baseline visits).

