11.4.3 Electrocardiograms

Standard 12-lead ECG recordings will be obtained after 10 minutes of rest in the supine or semirecumbent position. The following ECG variables will be reported together with the Investigator's interpretation of the ECG profile:

- PR interval
- QRS interval
- QT interval
- Heart rate
- QT corrected for heart rate using Fridericia's formula (QTcF)

The results of all ECG variables will be reported in the by-subject listings. The listing will also include the change from Baseline and will be presented by treatment group and visit.

Measured values and changes from Baseline will be summarized for each variable by treatment group and visit.

The following cut-points in QTcF (raw data and change from Baseline) will be summarized categorically by treatment group (number and percentage of subjects) and visit. The denominator for the percentages will be the number of subjects with a non-missing measurement for the variable at the specific visit.

Raw QTcF data:

- <450msec
- ≥ 450 msec to <480msec
- ≥ 480 msec to <500msec
- ≥ 500 msec

Change from Baseline QTcF:

- <30msec
- ≥ 30 msec to <60msec
- ≥ 60 msec

Electrocardiogram findings will be listed separately.

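### By-visit percentages of markedly abnormal laboratory and blood-pressure values at Weeks 24 and 28 are divided by the full Safety Set arm, including subjects no longer measured

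*SAP*

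**What the plan says.** SAP 3.1 gives the default: "Unless otherwise stated, the denominator for the percentages will be based on the number of subjects in the respective analysis set and treatment group". SAP 11 then fixes the analysis set: "All analysis of safety variables will be performed using the SS, unless otherwise stated". SAP 3.5.3 defines the Safety Set as "all subjects who received at least 1 dose of the study medication", so membership does not depend on still being in the study at a given visit.

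SAP 11.3 asks for "The number and percentage of subjects with treatment-emergent markedly abnormal (TEMA) laboratory results" by arm and visit. It also asks for shift tables of selected laboratory variables at every post-Baseline visit. SAP 11.4.1 asks for the number and percentage with markedly abnormal or potentially clinically significant vital signs (TEMA/PCS) at each visit and across all visits. Table 14-6 gives such criteria for systolic and diastolic pressure only. Neither section names a denominator or a missing category for these tables.

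Other sections do override the default. For the QTcF categories, SAP 11.4.3 says: "The denominator for the percentages will be the number of subjects with a non-missing measurement for the variable at the specific visit". HADS (8.3.4) and anti-drug antibodies (Section 10) also use the observations available at the visit. Where 8.3.2 keeps the full analysis-set denominator for the IGA shift and frequency tables, it requires a missing category.

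**The concern.** SAP 2.3 lets subjects who relapse enter the extension at Week 20, 24 or 28, after that visit's assessments. A subject who leaves at Week 20 has no Week 24 or Week 28 value in this study, and one who leaves at Week 24 has no Week 28 value. Both remain in the Safety Set denominator and cannot enter the numerator, so the table cannot separate a subject who was not abnormal from one who was not measured.

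Exit depends on PASI relapse, and the two arms differ in whether active drug is given at Week 16. Unequal exits are therefore plausible, and unequal exits would dilute the two columns of a side-by-side safety table by different amounts. The SAP recognises the issue for adverse events: 3.9 says a direct comparison of the arms needs a cut-off at Week 20, the first point of extension entry. The by-visit laboratory and blood-pressure percentages run past that point without any such device.

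**Working it through.** The documents give no percentage or exit rate for these tables, so there is no stated figure to reproduce. The check is to establish which denominator applies and then what it does.

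**Which denominator.** The default (3.1), the Safety Set for safety outputs (11) and the absence of an override in 11.3 and 11.4.1 together give the full Safety Set arm at every visit.

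**Which visits.**
- Week 20 is not affected by extension exits, because assessments come before leaving.
- Weeks 24 and 28 are affected by exits at earlier visits.
- Early withdrawals act in the same way once their early-withdrawal values have been mapped to one scheduled visit under SAP 4.4.
- Week 36 cannot be settled. SAP 2.3 requires the safety follow-up (SFU) assessments before extension entry, and Protocol Table 5-1 puts those in the same column as Week 36. SAP 4.4 assigns only early-withdrawal data to visits. If the SFU values taken at extension entry were placed at Week 36, leavers would count as measured there.

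**Formulas.** Let N be the Safety Set arm, m the number measured at the visit and x the number abnormal.
- Displayed = 100 × x/N
- Among those measured = 100 × x/m
- Hence displayed = (among those measured) × m/N

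**Inputs.** N = 30 in Arm A and 15 in Arm B (planned sizes, SAP 2.3). Exits before the visit are an assumption, ranged up to 50% in Arm A.

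**One abnormal subject (x = 1):**

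| Arm | Left | m | Displayed | Among measured |
|---|---|---|---|---|
| A | 3 (10%) | 27 | 1/30 = 3.3% | 1/27 = 3.7% |
| A | 6 (20%) | 24 | 3.3% | 1/24 = 4.2% |
| A | 9 (30%) | 21 | 3.3% | 1/21 = 4.8% |
| A | 15 (50%) | 15 | 3.3% | 1/15 = 6.7% |
| B | 2 | 13 | 1/15 = 6.7% | 1/13 = 7.7% |
| B | 3 | 12 | 6.7% | 1/12 = 8.3% |

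**Unequal exits.** Suppose both arms have the same 10% rate among those measured. This is a proportional illustration, not whole counts.

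| Left, A / B | A shown | B shown | Ratio A/B |
|---|---|---|---|
| 3 / 0 | 10 × 27/30 = 9.0% | 10 × 15/15 = 10.0% | 0.90 |
| 6 / 1 | 10 × 24/30 = 8.0% | 10 × 14/15 = 9.3% | 0.86 |
| 9 / 1 | 10 × 21/30 = 7.0% | 9.3% | 0.75 |
| 15 / 2 | 10 × 15/30 = 5.0% | 10 × 13/15 = 8.7% | 0.58 |

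Equal rates would look unequal, by an amount set only by the assumed exits.

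**The case against.** Much of the information can be recovered elsewhere. Counts accompany the percentages, and the descriptive summaries of the same variables report n by visit. Laboratory abnormalities are listed with all values of that variable, and vital-sign abnormalities are flagged in the listing. Section 5.1 tabulates extension entry by arm. Zero counts carry no percentage. The study is descriptive and not powered for conclusions on safety. All of this stands and limits the harm. It does not make the displayed percentage right, and the reader of these tables is not told how many were measured.

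The measured-subject denominator is not free of selection either: those still present at Weeks 24 and 28 have mostly not relapsed and left. The across-all-visits row keeps unequal follow-up whatever is done by visit. Both points stand. The change makes the percentage describe a stated group, but it does not make the arms comparable.

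A reader might infer that the ranking of the arms could reverse. With 3 abnormal of 30 in Arm A and 2 of 15 in Arm B, and 12 and 1 exits, the table shows 10.0% v 13.3%, against 3/18 = 16.7% v 2/14 = 14.3% among those measured. The arithmetic is correct, but the documents do not support the scenario for laboratory values. Markedly abnormal there means CTCAE Grade 3 or above, which Protocol 6.3 makes a reason for withdrawal. Under Protocol 6.4, a second subject meeting that or another listed criterion brings in the Data Monitoring Committee. Five such subjects at one late visit is not a routine cell. The blood-pressure criteria need both a threshold and a change from Baseline. No relapse rate supports 12 exits of 30 before Week 28.

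A reader might also infer that these tables are the SAP's only departure from measured-subject denominators. They are not: 8.3.2 uses the full analysis set for IGA, and the main PASI and IGA response tables keep everyone through nonresponder imputation. The difference is that those tables either show or impute the missing subjects.

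**Conclusion.** The concern holds for Weeks 24 and 28. A stated rule, not merely a missing detail, divides these by-visit percentages by subjects who have no measurement, and nothing in the tables shows it. The laboratory shift tables have the same gap.

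The size is modest. For one abnormal subject in Arm A, the understatement runs from 0.4 percentage points (3.7 − 3.3) to about 3.3 points (1/15 − 1/30 = 1/30) over assumed exits of 10% to 50%. Differential dilution between arms is conditional: it needs unequal exits, which the Week 16 contrast makes plausible but for which no rate is given. The documents do not establish which arm would be flattered. A claim that Week 36 is also diluted would go beyond the documents, because the visit assignment of the relevant assessments is undefined. To say that leavers are counted as normal describes the arithmetic effect, since the tables have no such category.

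**What to change.** In SAP 11.3 and 11.4.1, state that by-visit percentages, including those in the laboratory shift tables, use the number of subjects with a measured value of that variable at that visit, following the rule in 11.4.3. Print that n for each visit and arm. Keep the Safety Set count for the across-all-visits row. In SAP 4.4, state to which visit SFU assessments done at extension entry are assigned.

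Adding only a missing category over the full denominator, as 8.3.2 does for IGA, would expose the absences but leave the percentage diluted.

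The cost is one sentence in each of the two safety sections, one sentence on visit assignment, and a denominator and n change in the affected table programs. No new data are needed. The downside is that late-visit percentages will rest on smaller numbers and describe only subjects still in the study, which a footnote should say.
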